### **6.1.2 History and Physical Examination**

The relevant interval history should be obtained during screening and at the start of each cycle. Interval histories should include elicitation of interim illnesses and adverse events. If a subject remains on study treatment for more than 8 cycles, these assessments may occur every other month, see Section 9.

A problem-focused physical examination (PE) will be performed during screening, at the start of each cycle, on days 8 and 15 of cycle 1, and at the time of study discontinuation. If a subject remains on study treatment for more than 8 cycles, these assessments may occur every other month, see Section 9. Every PE should include measurement of body weight, vital signs, and evaluation of the ECOG performance score (see Appendix 1). Blood pressure must be recorded at each visit. Measurement of height need only occur at the screening PE.

### **6.1.3 Laboratory Examinations**

Laboratory examinations to be performed during screening include hemoglobin, white blood cell count including neutrophil count (sum of polysegmented granulocytes and band forms), platelets, bilirubin, alkaline phosphatase, ALT, AST, blood urea nitrogen (BUN), creatinine, calcium, electrolytes (sodium, potassium), and a urine pregnancy test (for women of child-bearing age).

Laboratory examinations are to be performed at the start of each cycle of treatment, on days 8 and 15 of cycle 1, and at the time of study discontinuation include hemoglobin, white blood cell count including neutrophil count (sum of polysegmented granulocytes and band forms), platelets, bilirubin, alkaline phosphatase, ALT, AST, blood urea nitrogen (BUN), creatinine, calcium and electrolytes (sodium, potassium).

## **6.2 Definition of Terms**

### **6.2.1 Adverse Event (AE)**

An adverse event (AE) is any undesirable sign, symptom or medical condition or experience that develops or worsens in severity after signing informed consent or any procedure specified in the protocol, even if the event is not considered to be related to the study.

Abnormal laboratory values or diagnostic test results constitute adverse events only if they induce clinical signs or symptoms or require treatment or further diagnostic tests.

CONFIDENTIAL

This document is confidential. Do not disclose or use except as authorized.

### 6.2.2 Serious adverse event (SAE)

A serious adverse event (SAE) is any adverse event, occurring at any dose and regardless of causality that:

- Results in death
- Is life-threatening. Life-threatening means that the person was at immediate risk of death from the reaction as it occurred, i.e., it does not include a reaction which hypothetically might have caused death had it occurred in a more severe form.
- Requires or prolongs inpatient hospitalization (i.e., the event required at least a 24-hour hospitalization or prolonged a hospitalization beyond the expected length of stay). Hospitalization admissions and/or surgical operations scheduled to occur during the study period, but planned prior to study entry are not considered SAEs if the illness or disease existed before the person was enrolled in the trial, provided that it did not deteriorate in an unexpected manner during the trial (e.g., surgery performed earlier than planned).
- Results in persistent or significant disability/incapacity. Disability is defined as a substantial disruption of a person's ability to conduct normal life functions.
- Is a congenital anomaly or birth defect; or
- Is an important medical event when, based upon appropriate medical judgment, it may jeopardize the participant and require medical or surgical intervention to prevent one of the outcomes listed above. Examples of such medical events include allergic bronchospasm requiring intensive treatment in an emergency room or at home; blood dyscrasias or convulsions that do not result in inpatient hospitalization, or the development of drug dependency or drug abuse.

Events **not** considered to be serious adverse events are hospitalizations for:

- routine treatment or monitoring of the studied indication, not associated with any deterioration in condition, or for elective procedures
- Abnormal lab values that do not require treatment
- treatment planned before signing informed consent for a pre-existing condition that did not worsen
- emergency outpatient treatment for an event not fulfilling the serious criteria outlined above and not resulting in inpatient admission
- respite care

### 6.2.3 Expected Adverse Events

Adverse events can be 'Expected' or 'Unexpected'. Expected adverse events are those that have been previously identified as resulting from administration of the agent. For the purposes of this study, an adverse event is considered expected when it appears in the Investigator's Brochure

### 6.2.4 Unexpected adverse event

For the purposes of this study, an adverse event is considered unexpected when it varies in nature, intensity or frequency from information provided in the Investigator's Brochure.

### 6.2.5 Attribution

Attribution is the relationship between an adverse event or serious adverse event and the study treatment. Attribution will be assigned as follows:

CONFIDENTIAL

This document is confidential. Do not disclose or use except as authorized.

- Definite – The AE is clearly related to the study treatment.
- Probable – The AE is likely related to the study treatment.
- Possible – The AE may be related to the study treatment.
- Unlikely - The AE is doubtfully related to the study treatment.
- Unrelated - The AE is clearly NOT related to the study treatment.

### **6.3 Procedures for AE and SAE Recording and Reporting**

Reporting or participating investigators will assess the occurrence of AEs and SAEs at all participant evaluation time points during the study.

All AEs and SAEs whether reported by the participant, discovered during questioning, directly observed, or detected by physical examination, laboratory test or other means, will be recorded in the participant's medical record and on the appropriate study-specific case report forms. Each recorded AE or SAE will be described by its duration (i.e., start and end dates), intensity treatment required, grade, suspected relationship to the investigational product (causality), outcome and actions taken with investigational product.

The descriptions and grading scales found in the CTEP NCI Common Terminology Criteria for Adverse Events (CTCAE) version 4.0 will be utilized for AE reporting. The CTCAE version 4.0 is located on the CTEP website at:

[http://ctep.cancer.gov/protocolDevelopment/electronic\\_applications/ctc.htm](http://ctep.cancer.gov/protocolDevelopment/electronic_applications/ctc.htm).

All appropriate treatment areas should have access to a copy of the CTEP Active Version of CTCAE.

To ensure consistency of AE and SAE causality assessments, investigators should apply the following general guideline:

- **YES**

There is a plausible temporal relationship between the onset of the AE and administration of the investigational product, and the AE cannot be readily explained by the patient's clinical state, intercurrent illness, or concomitant therapies; and/or the AE follows a known pattern of response to the investigational product; and/or the AE abates or resolves upon discontinuation of the investigational product or dose reduction and, if applicable, reappears upon re-challenge.

- **NO**

Evidence exists that the AE has an etiology other than the investigational product (e.g., preexisting medical condition, underlying disease, intercurrent illness, or concomitant medication); and/or the AE has no plausible temporal relationship to administration of the investigational product (e.g., cancer diagnosed 2 days after first dose of study drug).

Each participating investigator is required to abide by the reporting requirements set by the DF/HCC. The study must be conducted in compliance with FDA regulations, local safety reporting requirements, and reporting requirements of the principal investigator. Specific reporting requirements are detailed below.

#### **6.3.1 Serious Adverse Event Reporting**

##### **6.3.1.1 Reporting to the Institutional Review Board**

CONFIDENTIAL

This document is confidential. Do not disclose or use except as authorized.

All serious adverse events that occur, during treatment, or within 28 days of the last dose of treatment must be reported to the DFCI Office for Human Research Studies (OHRS). Events that occur after consent but before study enrollment/registration and receiving study treatment do not need to be reported. This includes events meeting the criteria outlined in Section 6.2.2, as well as the following:

- Grade 2 (moderate) and Grade 3 (severe) events that are unexpected and at least possibly related/associated with the intervention.
- All Grade 4 (life-threatening or disabling) events that are unexpected or not specifically listed in the protocol as not requiring reporting.
- All Grade 5 (fatal) events while the participant is enrolled and actively participating in the trial OR when the event occurs within 28 days of the last study intervention.

Note: If the participant is in long term follow up, report the death at the time of continuing review.

Participating investigators must report each serious adverse event within 24 hours of learning of the occurrence. In the event that the participating investigator does not become aware of the serious adverse event immediately (e.g., participant sought treatment elsewhere), the participating investigator is to report the event within 24 hours after learning of it and document the time of his or her first awareness of the adverse event.

Within the following 24-48 hours, the participating investigator must provide follow-up information on the serious adverse event. Follow-up information should describe whether the event has resolved or continues, if and how the event was treated, and whether the participant will continue or discontinue study participation.

#### **6.3.1.2 Reporting to Boehringer Ingelheim (BI)**

All AEs reported as an expedited Safety Report to the FDA, all other Serious adverse events and Non-serious AEs occurring at the same time and/or which are medically related to the SAE must also be reported to Boehringer Ingelheim using the BI SAE form per the timelines indicated in the Pharmacovigilance Agreement.

#### **6.3.1.3 Reporting to Hospital Risk Management**

Participating investigators will report to their local Risk Management office any subject safety reports or sentinel events that require reporting according to institutional policy.

#### **6.3.2 Non-Serious Adverse Event Reporting**

Non-serious adverse events will be reported on the toxicity Case Report Forms.

### **6.4 Monitoring of Adverse Events and Period of Observation**

CONFIDENTIAL

This document is confidential. Do not disclose or use except as authorized.

All adverse events, both serious and non-serious, and deaths that are encountered from signing of the informed consent, throughout the study, and within 28 days of the last study intervention should be followed to their resolution, or until the participating investigator assesses them as stable, or the participating investigator determines the event to be irreversible, or the participant is lost to follow-up. The presence and resolution of AEs and SAEs (with dates) should be documented on the appropriate case report form and recorded in the participant's medical record to facilitate source data verification.

For some SAEs, the study sponsor or designee may follow-up by telephone, fax, and/or monitoring visit to obtain additional case details deemed necessary to appropriately evaluate the SAE report (e.g., hospital discharge summary, consultant report, or autopsy report).

Participants should report any serious post-study event(s) that might reasonably be related to participation in this study, including any unanticipated death or adverse event occurring after a participant has discontinued or terminated study participation that may reasonably be related to the study.

## **6.5 Contraception and Pregnancy**

Female patients who are not of childbearing potential due to being postmenopausal (2 years without menses) or surgical sterilization (oophorectomy, hysterectomy and/or tubal ligation) do not need to use contraception. All other female patients are considered to have childbearing potential and should use adequate contraception throughout the study (from screening until end of study participation or 28 days after last dose of trial medication, whichever is later).

Acceptable methods of contraception for females include hormonal contraception and double barrier method. Double barrier method of contraception is defined as two barrier methods used simultaneously each time the patient has intercourse. Accepted barrier methods include diaphragm, female condom, cervical cap, male condom and IUD (the diaphragm and cervical cap must be used in conjunction with spermicidal jelly/cream). If hormonal contraceptives are used, at least one barrier method should also be used. Partner vasectomy, natural 'rhythm' and spermicidal jelly/cream are not acceptable as methods of contraception.

Male patients should use adequate contraception throughout the study (e.g. condom and spermicidal jelly).

Female patients must have a negative pregnancy test ( $\beta$ -HCG test in urine or serum) prior to commencing study treatment. If a patient is found to be pregnant during study participation, this should be handled as follows:

CONFIDENTIAL

This document is confidential. Do not disclose or use except as authorized.

Timing of Pregnancy	Action
Prior to starting study medication	Patient should be withdrawn from the study immediately. No reporting necessary.
During study treatment	Treatment must be stopped immediately and the pregnancy should be reported immediately using the pregnancy form.  If the investigator wishes to give any further treatment with study medication, this must be discussed and agreed with Boehringer Ingelheim.
During follow-up (after finishing treatment but before end of study participation), or within 28 days of last dose of study medication (even if no longer participating in study)	The pregnancy should be followed up to final outcome including any premature termination. Only reports of premature termination should be reported to the Boehringer Ingelheim on the BI SAE form.  In addition, any event leading to the termination of pregnancy (i.e. spontaneous, accidental, or induced abortion; as well as miscarriage, intrauterine fetal demise/death) must be reported as an SAE.

CONFIDENTIAL

This document is confidential. Do not disclose or use except as authorized.

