In oral repeated dose studies for up to 26 weeks in rats and minipigs, the main target organs were the gastrointestinal tract (rats and minipigs), kidneys (rat), and the skin (rats). In the gastrointestinal tract, increasing systemic exposure was associated with dose-dependent atrophy of the epithelium and concomitant focal erosions/ulcerations in the stomach of rats and minipigs. Clinically this resulted in diarrhea in both species and fecal occult blood in a single minipig. In rat kidneys papillary necrosis and dilated tubules were found. Similar pathologic findings, i.e., papillary necrosis in rats and dogs have been described previously for the EGFR-small molecule inhibitor gefitinib. However, nephrotoxicity has not been reported as a side-effect of gefitinib therapy in humans. A secondary pathophysiologic effect on renal function in BIBW 2992-treated animals due to diarrhea-induced dehydration and emaciation has to also be considered. Cutaneous alterations, i.e., epithelial atrophy were observed in rats. However, BIBW 2992 is not irritating to intact skin in albino rabbits and the effects observed in rats are most likely related to the specific pharmacodynamic mechanism of EGFR-inhibition (ref investigator's brochure). A variety of organs including the aerodigestive tract and reproductive organs were affected by epithelial atrophy. These atrophic changes were not severe and fully reversed during a 2-week recovery period. Minor cardiovascular effects (increased blood pressure and heart rate) and a dose-dependent decrease of QT time in the electrocardiogram (ECG) occurred in BIBW 2992-treated minipigs. These data do not indicate a risk for QT-prolongation related arrhythmia. BIBW 2992 had no pro-arrhythmic potential, as determined by the effects on HERG-mediated potassium current or on guinea pig papillary muscle action potential configuration. BIBW 2992 demonstrated mutagenic potential in bacteria but had no genotoxic potential *in vivo* even at highly toxic/lethal doses in animals. Because of its specific pharmacodynamic mechanism of action, BIBW 2992 is potentially embryo/fetotoxic and/or teratogenic.

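### The pregnancy table in Section 6.5 limits supplier SAE-form reports to premature terminations, which contradicts the protocol's own SAE definition (6.2.2) and its rule that all SAEs go to the supplier (6.3.1.2)

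*Combined protocol and SAP*

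**What the plan says.** The pregnancy table in Section 6.5 sets out actions by the time at which a pregnancy is found.

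- **Found on treatment:** "Treatment must be stopped immediately and the pregnancy should be reported immediately using the pregnancy form". The row does not say who receives the form or what is done about the outcome.
- **Found later:** the row is labelled "During follow-up (after finishing treatment but before end of study participation), or within 28 days of last dose of study medication". Its cell first says "The pregnancy should be followed up to final outcome including any premature termination" and then "Only reports of premature termination should be reported to the Boehringer Ingelheim on the BI SAE form". A further sentence in the cell requires events that lead to a termination to be reported as SAEs.

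Three other parts of the protocol bear on the same event.

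- **SAE definition:** among the criteria in Section 6.2.2 is "Is a congenital anomaly or birth defect; or". Appendix 3, Section 6.1, also includes this outcome.
- **Supplier reporting (6.3.1.2):** SAEs "must also be reported to Boehringer Ingelheim using the BI SAE form". The section has no pregnancy exception and no time window, and leaves timelines to the Pharmacovigilance Agreement.
- **IRB reporting (6.3.1.1):** "All serious adverse events that occur, during treatment, or within 28 days of the last dose of treatment must be reported".

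Section 2.1.2 states that "BIBW 2992 is potentially embryo/fetotoxic and/or teratogenic".

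**The concern.** A congenital anomaly is an SAE by definition, and every SAE is owed to the supplier on the BI SAE form. The pregnancy table says that, of pregnancy reports, premature terminations alone go on that form. Both instructions cannot be followed for a live birth with a malformation.

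The table is the more specific text, and it is where site staff will look when a pregnancy occurs. Nothing in the protocol says that 6.3.1.2 prevails over it. What is at stake is whether the supplier learns of the pregnancy outcome that matters most for a drug with acknowledged teratogenic potential. The estimates of T790M proportion, response and survival are not involved.

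**Working it through.** The point rests on no sample size, power or event count, so the check sets the sections side by side for one case: a pregnancy followed to delivery, with a malformed live-born child.

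1. **Is it an SAE?** Yes, under Section 6.2.2 and again under Appendix 3, Section 6.1.

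2. **Does 6.3.1.2 send it to the supplier?** Yes. Its scope is all SAEs, and the form and recipient are the same ones the table restricts.

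3. **Does the 6.5 table send it?** No, if read literally. The outcome is not a premature termination. The additional SAE sentence in the cell covers events leading to termination, so it does not bring back a live birth with an anomaly.

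4. **Would the site know of it?** In the follow-up row, yes, because the same cell asks for follow-up to the final outcome. The site would learn of the defect and then read that the supplier form is for terminations alone.

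5. **Would the IRB route catch it?** Usually not. The 6.3.1.1 window closes 28 days, or 28 / 7 = 4 weeks, after the last dose. A defect found at birth falls inside it only if delivery comes within four weeks of the last dose. Section 6.5 requires a negative pregnancy test before treatment starts, and treatment stops when a pregnancy is found, so delivery will usually be later. It is usually rather than always, because the on-treatment row allows further dosing if the supplier agrees.

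6. **Would another route catch it?** Not reliably.
   - Section 6.4 follows adverse events that arise up to 28 days after the last intervention.
   - The adverse event form in Appendix 3, Section 4.10.5, runs to 30 days after the last dose.
   - Section 6.4 also asks participants to report serious post-study events that may be related, but sets the site no onward duty, form or deadline.
   - Appendix 3, Section 6.2, routes SAEs to the supplier and the FDA, but only those that meet the reporting criteria, and it has no separate pregnancy route.

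Steps 2 and 3 are the contradiction. Steps 5 and 6 show that the remaining routes do not dependably resolve it.

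**The case against.** The strongest reply is that 6.3.1.2 already requires the report, with no exception and no time limit. That stands, and it rules out one tempting reading. A reader might infer that the protocol leaves birth defects unreported as a rule. It does not: one section requires the report and another, read literally, excludes it.

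A second reply is that the restriction merely sorts paperwork: a pregnancy as such goes on the pregnancy form, and a termination goes on the SAE form. This reading is possible, but it does not remove the conflict, because the one sentence in the cell that adds SAE reporting is confined to events leading to termination.

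A third reply concerns scope. A reader might infer that the restriction governs every exposed pregnancy, and also that pregnancies found on treatment are not followed to outcome. The two sentences concerned stand next to each other in one cell, so those inferences cannot both hold. If the cell belongs to the follow-up row alone, the restriction does not reach on-treatment pregnancies. If it spans both rows, so does the follow-up. The table breaks at exactly this place in the text as read from the PDF, so the row boundary is uncertain. The conflict with 6.2.2 and 6.3.1.2 stands either way.

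Finally, the pregnancy form and the Pharmacovigilance Agreement are not in the documents, so what else reaches the supplier through them cannot be checked. The 28-day limit concerns the IRB office and does not by itself show that the supplier is not told.

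**Conclusion.** The concern holds as an internal contradiction in safety reporting. The restriction in the 6.5 table conflicts with 6.2.2, with Appendix 3 and with 6.3.1.2. A site that follows the table literally would not send a birth defect to the supplier, and the IRB rule would usually not catch it.

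Its practical size is small in count. Pregnancies are assumed to be rare among the 24 patients given in Section 12.1, and the documents offer no figure for them. Its consequence could be serious for any pregnancy affected, given Section 2.1.2. Efficacy results are unaffected. The conclusion assumes that no document outside the protocol, such as the Pharmacovigilance Agreement, overrides the table. It should be corrected, but as a wording fault rather than a flaw in the trial's design.

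**What to change.** Reconcile Section 6.5 with 6.2.2 and 6.3.1.2 in three steps.

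1. Remove the restriction from the table, so that a congenital anomaly or birth defect, like any other outcome meeting 6.2.2, is reported to the supplier on the BI SAE form.
2. State how an anomaly found after the 28-day window reaches the supplier and, in line with DFCI IRB requirements, the IRB. Those requirements are not in the documents, so the text should refer to them rather than create an unlimited IRB reporting rule.
3. Confirm that follow-up to final outcome also applies to pregnancies found during treatment, since the table as read leaves this unclear.

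The cost is a few lines of protocol wording, submitted as an amendment under Section 11.1. Sample size, study treatment and other patients' visits do not change.
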